# 6.1. Overall Study Design

Approximately 27 patients who have provided written informed consent, and have met all the inclusion criteria and none of the exclusion criteria, will be enrolled in the study, with the aim of having at least 6 patients in each cohort completing the study.

Patients will be seen for a Screening visit and will be evaluated after the patient (or legal guardian) provides written informed consent. The Screening visit will include assessments to confirm the diagnosis of HPP, including medical history to confirm onset of HPP symptoms prior to age 18. Patients who fail any of the eligibility criteria may be re-screened only after discussion with the Medical Monitor.

After completion of the Screening visit, patients who meet inclusion/exclusion criteria for Study AA-HPP-208 will be randomized in a 1:1:1 ratio to 1 of the following 3 cohorts:

- **Cohort 1:** Asfotase alfa 0.5 mg/kg initial single dose; followed by multiple dosing starting after 2 weeks at 0.5 mg/kg 3 times per week
- **Cohort 2:** Asfotase alfa 2.0 mg/kg initial single dose; followed by multiple dosing starting after 2 weeks at 2.0 mg/kg 3 times per week
- **Cohort 3:** As fotase alfa 3.0 mg/kg initial single dose; followed by multiple dosing starting after 2 weeks at 3.0 mg/kg 3 times per week

Randomization will be stratified by gender to ensure a similar distribution of gender in each cohort.

Patients will receive a single dose on Week 1, Day 1; on Week 3, Day 1 (Study Day 15) patients will start multiple dosing with the 3 times per week regimen as described above. All doses will be administered as subcutaneous (SC) injections throughout the study.

[figure not shown]

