(3 times per	Week 4	Day 22: pre-dose, post-dose 6h	D22, D24, D26	All	Day 22: pre-dose
week)	Week 5	Day 29: pre-dose (trough), post-dose 6h	D29, D31, D33	All	Day 29: pre-dose
	Week 6	None	D36, D38, D40	None	None
	Week 7	Day 43: pre-dose (trough), post-dose 6h	D43, D45, D47	All	Day 43: pre-dose
	Week 8	Day 50: pre-dose (trough), post-dose 6h	D50, D52, D54	All	Day 50: pre-dose
	Week 9	Day 57: pre-dose Day 61: pre-dose (trough), post-dose 6h, 12h Day 62:post-D61 dose 24h, 32h, 36h, Day 63:post-D61 dose 48h, 56h, 60h	D57, D59, D61	All	Day 61: pre-dose
No Dosing	Week 10	Day 64: post-D61 dose 72h Day 65: post-D61 dose 96h Day 66: post-D61 dose 120h Day 67: post-D61 dose 144h Day 68: post-D61 dose 168h	None	All	Day 68: post-D61 dose 168h
	Week 11	Day 71: post-D61 dose 240h Day 75: post-D61 dose 336h	None	All	Day 75: post-D61 dose 336h
	Week 12	Day 80: post-D61 dose 456h	None	All	Day 80: post-D61 dose 456h
	Week 13	Day 87: post-D61 dose 624h	None	All	Day 87: post-D61 dose 624h

Abbreviations: ADA = anti-drug antibodies; PK = pharmacokinetics; PLP = pyridoxal 5'-phosphate; PPi = inorganic pyrophosphate; SOM = Study Operations Manual; D = day; h = hour

NOTE: Trough is defined as pre-dose concentration (ie, concentration data-point collected just prior to the next dose).

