## 11.5.8. Statistical Methods: Power and Sample Size

A sample size of 9 patients per cohort (27 patients total) will provide sufficient power (>80%) to detect a difference of 2.3 μM between the 9.0 mg/kg/week cohort compared to the 1.5 mg/kg/week cohort, and between the 6.0 mg/kg/week cohort compared to the 1.5 mg/kg/week cohort in the change from Baseline to pre-3rd dose in Week 9 PPi (assuming a SD of 1.5 μM). This is based upon the use of a 2-sided, 2-sample t-test analyzed using a fixed sequence testing procedure with the comparison of the 9.0 mg/kg/week cohort compared to the 1.5 mg/kg/week cohort being performed first, and the hypothesis testing for the second comparison 6.0 mg/kg/week cohort compared to the 1.5 mg/kg/week cohort only being performed if the null hypothesis is rejected for the previous comparison at a significance level of 0.05.

A sample size of 6 patients per cohort (18 patients total) will provide sufficient power (>90%) to detect a difference of 3.2  $\mu$ M (SD 1.5  $\mu$ M) using the same assumptions and fixed sequence testing procedure. A difference of 3.2  $\mu$ M (SD 1.5  $\mu$ M) was observed in adult pediatric-onset treated patients versus controls in Study ENB-009-10 for the change from baseline to Week 6 in

PPi. Between 6 and 9 patients per cohort (18 and 27 patients total) will give sufficient power to detect a mean difference of 2.3 to 3.2  $\mu$ M (SD 1.5  $\mu$ M).

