#### 7.2.1. Primary Endpoint

The primary endpoint for this study is the change in PPi from Baseline to pre-3rd dose Week 9. Change from Baseline in PPi will be the primary variable. Primary analysis will be performed by using a restricted maximum likelihood (REML)-based repeated measures mixed model, fit for each treatment cohort to estimate the change at each pre-dose (trough) timepoint starting at Week 4 (Day 22) through Week 9 (Day 61). The primary hypotheses will test whether the differences between the cohorts differ from zero at pre-3rd dose Week 9. The Week 3 (Day 15) pre-dose timepoint will not be included in the model assessing change since this is expected to be similar to a baseline level of PPi after the first non-dosing period. The analysis will include the fixed, categorical effect of visit, adjusted for baseline PPi, gender, baseline weight group ( $\geq$  median versus < median), and study drug lot assignment. An unstructured covariance structure will be used to model the within-patient errors. If this analysis fails to converge, the following structures will be tested and the final covariance structure will be determined by Akaike's information criterion (AIC): first-order autoregressive, compound symmetry, and Toeplitz. The Kenward-

Roger approximation will be used to estimate denominator degrees of freedom. The estimated mean change from Baseline at each visit from the model will be provided, along with 95% CIs and p-values.

A fixed sequence testing procedure will be performed with the comparison of the 3.0 mg/kg cohort compared with the 0.5 mg/kg cohort being performed first, and the hypothesis testing for the second comparison 2.0 mg/kg cohort compared with the 0.5 mg/kg cohort only being performed if the null hypothesis is rejected for the previous comparison at a significance level of 0.05 (p-value <0.05). The primary endpoint will be met if the null hypothesis is rejected for both comparisons at a significance level of 0.05 (both p-values <0.05).

The same model will additionally be employed with the fixed, categorical effect of visit, adjusted for baseline PPi.

A similar modeling approach will be employed to explore the effect of treatment cohort on the change from Baseline in PPi at each pre-dose timepoint.

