#### 7.2.1.4. Hypothesis Testing and Significance Level

A two-sided Type I error rate of 0.05 will be used to define statistical significance. The primary endpoint will be met if the null hypothesis is rejected for both comparisons described in Section 7.2.1 at a significance level of 0.05, i.e. both p-values <0.05. For the primary endpoint, a fixed sequence testing procedure will be used to control the Type I error rate. Statistical adjustment of p-values will not be performed.

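### If the unstructured model fails to converge, every named fallback covariance forces one variance on all visits, so the deciding Day 61 test may not hold its 5% level

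*SAP*

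**What the plan says.** SAP 7.2.1 fits a REML repeated-measures model to the change in PPi at the pre-dose visits from Day 22 to Day 61. It describes the model as fitted for each cohort and tests the cohort differences at the pre-third-dose sample of Week 9 (Day 61). The covariance is unstructured. If that does not converge, the candidates are "first-order autoregressive, compound symmetry, and Toeplitz", chosen by AIC, with Kenward-Roger degrees of freedom. No heterogeneous-variance version and no robust variance is named. Protocol 11.5.4.1 has the same list, but there the mixed model is an additional analysis and the Wilcoxon rank-sum test is primary. SAP 4.1 reverses those roles.

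Protocol Table 3 schedules the Week 9 samples as "Day 57: pre-dose Day 61: pre-dose (trough), post-dose 6h, 12h". Doses are given on Mondays, Wednesdays and Fridays (Protocol 6.1, note). SAP 7.2.1.4 sets the level: "A two-sided Type I error rate of 0.05 will be used to define statistical significance". Protocol 11.5.8 plans the study "assuming a SD of 1.5" μM, a single value with no breakdown by visit. Protocol 6.1 allocates about 27 patients equally between the three arms and states its completion target as "with the aim of having at least 6 patients in each cohort completing the study".

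**The concern.** The standard error of the Day 61 contrast depends on the variance that the model assigns to Day 61. The unstructured model estimates it freely. The three fallbacks replace it with one value pooled over all six visits.

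There are reasons to doubt equal variances. Day 61 has a shorter interval since the last dose than any other modelled visit. Day 22 follows only one week of repeated dosing. Values below the quantification limit are set to 0.75 μM (SAP Table 4), and this floor could compress the spread more at some visits than at others. If the Day 61 variance is larger than the pooled value, the primary p-value is too small; if it is smaller, the test loses power. Kenward-Roger corrects for small samples within the assumed structure. It does not repair a wrong structure.

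**Working it through.** **The plan's own figures.** For a two-sided two-sample t-test, the noncentrality is difference / (SD × √(2/n)), with 2n − 2 df.
- n = 9, 2.3 μM: 2.3 / (1.5 × √(2/9)) = 3.25, 16 df, power 86.3%. The plan says this size "will provide sufficient power (>80%) to detect a difference of 2.3" μM.
- n = 6, 3.2 μM: 3.2 / (1.5 × √(2/6)) = 3.70, 10 df, power 91.4%. The plan says "A sample size of 6 patients per cohort (18 patients total) will provide sufficient power (>90"%).

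Both bounds hold per comparison. They rest on a single SD, so they do not bear on equality of variance across visits.

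**Schedule (Protocol Table 3).**

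| Visit (day) | 22 | 29 | 43 | 50 | 57 | 61 |
|---|---|---|---|---|---|---|
| Previous dose (day) | 19 | 26 | 40 | 47 | 54 | 59 |
| Hours since dose | 72 | 72 | 72 | 72 | 72 | 48 |
| Days since previous visit | – | 7 | 14 | 7 | 7 | 4 |

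Table 3 does not label Day 57 as a trough. If it were left out, Day 61 would still be the only 48 h sample.

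**How likely the fallback is.** Unstructured over six visits has 6 × 7 / 2 = 21 parameters. In a per-cohort fit with visit means only, 9 patients leave residual rank 8. Six patients leave rank 5, below the 6 that a 6 × 6 matrix needs. Covariates reduce this further. Partial data from patients who drop out may help. A fit across all three cohorts does not have the rank problem.

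**Effect of a common variance.** Let r be the Day 61 SD divided by the SD σ at the other five visits. With complete data, cohort-by-visit means and compound symmetry, the fitted variance is the average, σ²(5 + r²)/6, while the true Day 61 variance is σ²r². In large samples the single-comparison error is

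2 × {1 − Φ(c)}, with c = 1.96 × √((5 + r²)/6) / r.

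- r = 0.8: (5 + 0.64)/6 = 0.940; c = 1.96 × 0.9695 / 0.8 = 2.375; error 1.8%.
- r = 1.25: (5 + 1.5625)/6 = 1.094; c = 1.96 × 1.0458 / 1.25 = 1.640; error 10.1%.
- r = 1.5: (5 + 2.25)/6 = 1.208; c = 1.96 × 1.0992 / 1.5 = 1.436; error 15.1%.

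**Simulation** (3.0 versus 0.5 mg/kg at Day 61, null true, 9 per cohort, pooled fit, complete data, correlation decaying with actual days at 0.6 or 0.85 per week). Satterthwaite df stood in for Kenward-Roger and covariates were omitted. The AIC and unstructured columns use 1,500 trials per case (Monte Carlo SE about 0.6 points). The compound symmetry column uses 20,000.

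| r (assumed) | AIC choice of the three | Compound symmetry | Unstructured |
|---|---|---|---|
| 0.8 | 2.5% | 1.8% | 4.8% |
| 1.0 | 3.9–4.4% | 5.3% | 3.7–4.6% |
| 1.25 | 9.0–9.5% | 10.3% | 5.1–5.6% |
| 1.5 | 11.7% | 14.9% | 4.9% |

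A further simulation with 24 df fixed gave 7.8% at r = 1.25 and 1.9% at 0.8. With 6 per cohort and r = 1.25, the AIC choice gave 8.5%. In the 20,000-trial runs, giving Day 61 its own variance returned 4.9–5.3% throughout.

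**Spacing alone (r = 1).** Complete data: AR(1) 4.0–4.4%, Toeplitz 3.8–4.4%. With about 33% random dropout: AR(1) 5.3–5.5%, against 5.5–5.6% for a spatial-power structure on actual days.

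**Both comparisons.** The two contrasts share the 0.5 mg/kg cohort, so their correlation is 0.5. With both nulls true, the bivariate normal probability that both exceed c in absolute value is 2.5% at c = 1.640 and 4.4% at c = 1.436.

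**The case against.** The strongest reply is that the harm depends on an input that the documents do not supply. A shorter dosing interval may shift the mean trough without changing the between-patient SD. If the SD is the same at every visit, the fallbacks hold their level. This stands: neither the size nor the direction of the error is known.

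The rank argument applies to per-cohort fits, while the error rates come from a pooled fit. That also stands. Six is a floor on patients completing the study at Week 13, not a forecast of Day 61 values, so failure of the unstructured model is a prospect and not a certainty.

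Success needs both comparisons to reject, and with both nulls true that stays below 5% at the ratios examined. But if one comparison has a large true effect and the other has none, false success approaches the single-comparison rate.

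The exact Wilcoxon test (SAP 7.2.1) and the ANCOVA (SAP 7.2.1.5) analyse Day 61 without this covariance, so a discrepancy would show. They are supportive and sensitivity analyses and cannot replace the primary p-value.

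A reader might infer that the uneven visit gaps invalidate the fallbacks. The schedule does not support that. Compound symmetry makes no use of spacing. For AR(1) and Toeplitz, which do assume equal steps, spacing alone barely moves the Day 61 test.

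**Conclusion.** The point holds as a conditional weakness in the primary analysis. If the unstructured model fails and the Day 61 SD differs from the other visits, the single-comparison type I error is about 8–10% at a ratio of 1.25, 12–15% at 1.5 and 2–2.5% at 0.8. These figures assume 9 per cohort, a pooled fit, complete data and no covariates, and the ratios are assumptions. It would be too strong to say that the test is anticonservative, or that the trial's false-success rate is 10%: the documents fix neither the direction nor the size of the variance difference. It is still worth acting on, because the deciding test should not depend on an equal-variance assumption that the plan does not justify and can avoid by a change of wording.

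**What to change.** In SAP 7.2.1, replace the fallback list with structures that keep a separate variance for each visit, tried in a fixed order: for example first-order antedependence (ANTE(1)), then heterogeneous Toeplitz or ARH(1), then heterogeneous compound symmetry. Do not use equal-variance spatial power on study day as a fallback. It corrects the spacing but keeps the common variance: with 33% dropout and a ratio of 1.25 it gave 10.8%, against 9.9% for AR(1) and 12.9% for compound symmetry.

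The cost is SAP wording and some extra covariance parameters: 6 variances + 5 correlations = 11 for ANTE(1), and 6 + 1 = 7 for heterogeneous compound symmetry, against 2 for AR(1) or compound symmetry and 6 for Toeplitz. A fit using all three cohorts can support this; a fit within one small cohort may not, so the SAP should say which fit supplies the covariance. The error rates of the named heterogeneous structures were not simulated one by one. The near-nominal results come from the unstructured fit and from using Day 61's own variance. Keep the Wilcoxon and ANCOVA analyses as supportive checks.

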#### 7.2.1.1. Handling of Dropouts or Missing Data

The protocol schedule requires 5 pre-treatment baseline PPi samples (-168, -156, -24, -12h, and pre-dose Day 1) be collected. The average value will be used for calculating Baseline PPi; therefore, at least 1 pretreatment baseline observation is required for the patient to be included for the assessment of the primary analysis. Patients will also be required to have at least 1 on-treatment PPi observation to be included in the FA Set. For the analyses of changes from Baseline using repeated measures mixed modeling, missing values will not be imputed based on a Missing at Random Assumption (MAR). Missing values at the pre-3rd dose Week 9 assessment will be imputed with the last available on-treatment pre-dose trough assessment prior to pre-3rd dose Week 9 using LOCF. This imputation will occur where indicated.

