#### NOTE: Baseline definitions:

• For PD assessments, there are 5 pre-treatment baseline samples (-168, -156, -24, -12, and 0h) to be collected. The average value will be used for Baseline.

- For PK and immunogenicity assessments, Baseline is Day 1 pre-dose sample.
- Timepoints for pre-dose PK sample collection have a window of -15 minutes and for post-dose PK sample collection have a window of ±15 minutes. For additional instructions, please refer to the SOM.
- 2 The Week 1, Day 1 single dose must be administered on a Monday, and the multiple dosing in Week 3 through Week 9 must be administered on Mondays, Wednesdays, and Fridays.

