As supportive analysis, the non-parametric exact Wilcoxon rank-sum test will be used to assess differences between treatment cohorts, using both last observation carried forward (LOCF) and observed case (OC) methods. The location shift in the change from Baseline distributions and 95% CI for the above comparisons will be reported using the Hodges-Lehmann-Sen estimate and the exact confidence limits reported.

To examine the change from Baseline in PPi, descriptive statistics for the absolute PPi level and the change from Baseline will be summarized at all study timepoints by treatment cohort, spanning from Week 1 to Week 13; Baseline will be calculated in the same way as for the primary analysis. Within cohort, the change from Baseline to all study timepoints will be analyzed using the non-parametric Wilcoxon signed-rank test.

Individual and mean PPi levels for each cohort versus time curves will be presented with normal references ranges indicated (see Appendix 9.3). Please refer to Table 4 on how to handle the values fall under the lower limit of quantification (LLOQ). Additional analysis of PPi data may be performed if considered useful.

The above analyses for PPi will additionally be performed using the PP Set.

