#### 7.2.1.5. Sensitivity Analyses

The change in PPi from Baseline to pre-3rd dose Week 9 will also be analyzed using analysis of covariance (ANCOVA), with treatment as fixed factor, baseline PPi, gender, baseline weight group ( $\geq$  median versus < median), and study drug lot assignment as covariates, and using both LOCF and OC methods in the FA Set.

The tests will compare 2.0 mg/kg cohort to 0.5 mg/kg cohort, and 3.0 mg/kg cohort to 0.5 mg/kg cohort. Ninety-five percent CIs will be presented together with the estimated p-values.

In addition, sensitivity analyses will be performed if any medications are administered to the patient that might impact the results used in the primary analysis of PPi.

Sensitivity analyses may be employed that include only the patients that receive 100% of the study drug doses through Week 9, as specified in the protocol.

Finally, sensitivity analyses may be employed to exclude biologically implausible outliers in PPi and PLP.

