-  A full ophthalmology examination will be performed at scheduled visits. The examination will assess for papilledema and signs of ectopic calcification, and will include assessments of visual acuity; adnexa; and slit-lamp biomicroscopy with examination of anterior chamber, lens, conjunctiva, cornea, and fundus. The ophthalmology examination should be performed by a qualified ophthalmologist. Sites will be provided ophthalmologic worksheets required to complete the full exam. Ophthalmology exams may be performed by a qualified optometrist (i.e., Doctor of Optometry, O.D.) as long as the optometrist works under the supervision of an ophthalmologist.
-  Asfotase alfa anti-drug antibody testing and PK/PD analyses must be performed on samples obtained at the same time (ie, predose samples from the same study visit).
-  Refer to Table 3 for timing of PK/PD and asfotase alfa anti-drug antibody assessments.
-  For acute or severe IARs (eg, with signs/symptoms of hypersensitivity, irrespective of the time from administration of study drug to onset), additional blood and urine samples must be collected to assess the reaction. Refer to Section 9.5 for details of sample collection.

				PK, PPi	
	Week	Sampling Times	Dosing 	and PLP	ADA
Run-in	Week -1	Day -7: -168h, -156h pre-dose	NA	PPi and	NA
Period	(establish	Day -1: -24h, -12h pre-dose		PLP only	
	baseline)				
Single	Week 1	Day 1: pre-dose; post-dose 6h, 12h	D1 (single-	All	Day 1: pre-dose
Dose			dose)		
No Dosing	Week 1	Day 2: post-D1 dose 24h, 32h, 36h	None	All	
		Day 3: post-D1 dose 48h, 56h, 60h			
		Day 4: post-D1 dose 72h			
		Day 5: post-D1 dose 96h			
		Day 6: post-D1 dose 120h			
		Day 7: post-D1 dose 144h			
No Dosing	Week 2	Day 8: post-D1 dose 168h	None	All	Day 8: post-D1 dose
0		Day 11: post-D1 dose 240h			168h
Weekly	Week 3	Day 15: pre-dose, post-dose 6h	D15, D17,	All	Day 15: pre-dose
Dosing			D19		
(3 times	Week 4	Day 22: pre-dose, post-dose 6h	D22, D24,	All	Day 22: pre-dose
per week)			D26		
	Week 5	Day 29: pre-dose (trough), post-	D29, D31,	All	Day 29: pre-dose
		dose 6h	D33		
	Week 6	None	D36, D38,	None	None
			D40		
	Week 7	Day 43: pre-dose (trough), post-	D43, D45,	All	Day 43: pre-dose
		dose 6h	D47		
	Week 8	Day 50: pre-dose (trough), post-	D50, D52,	All	Day 50: pre-dose
		dose 6h	D54		
	Week 9	Day 57: pre-dose	D57, D59,	All	Day 61: pre-dose

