# Table 3: Protocol schedule of events for Pharmacokinetic, Pharmacodynamic, andImmunogenicity Assessments

	Week	Sampling Times	Dosing 	PK, PPi and PLP	ADA
		Day 61: pre-dose (trough), post- dose 6h, 12h, 24h, 32h, 36h, 48h, 56h, 60h	D61		
No Dosing	Week 10	Day 64: post-D61 dose 72h Day 65: post-D61 dose 96h Day 66: post-D61 dose 120h Day 67: post-D61 dose 144h Day 68: post-D61 dose 168h	None	All	Day 68: post-D61 dose 168h
	Week 11	Day 71: post-D61 dose 240h Day 75: post-D61 dose 336h	None	All	Day 75: post-D61 dose 336h
	Week 12	Day 80: post-D61 dose 456h	None	All	Day 80: post-D61 dose 456h
	Week 13	Day 87: post-D61 dose 624h	None	All	Day 87: post-D61 dose 624h

Abbreviations: ADA = anti-drug antibodies; PK = pharmacokinetics; PLP = pyridoxal 5'-phosphate; PPi = inorganic pyrophosphate; SOM = Study Operations Manual; D = day; h = hour, NA=not applicable.

NOTE: Trough is defined as pre-dose concentration (ie, concentration data-point collected just prior to the next dose). NOTE: Baseline definitions:

• For PD assessments, there are 5 pre-treatment baseline samples (-168, -156, -24, -12, and pre-dose Day 1) to be collected. The average value will be used for Baseline.

• For PK and immunogenicity assessments, Baseline is Day 1 pre-dose sample.

1 Timepoints for pre-dose PK sample collection have a window of -15 minutes and for post-dose PK sample collection have a window of  $\pm 15$  minutes. For additional instructions, please refer to the SOM.

2 The Week 1, Day 1 single dose must be administered on a Monday, and the multiple dosing in Week 3 through Week 9 must be administered on Mondays, Wednesdays, and Fridays.

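### Does the SAP's carry-forward rule for a missing Day 61 PPi need a fixed list of source samples?

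*SAP*

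**What the plan says.** The primary analysis in SAP 7.2.1 is a repeated measures mixed model on the pre-dose values from Day 22 to Day 61. Under SAP 7.2.1.1 it imputes nothing and relies on missing at random. Of Day 15, SAP 7.2.1 says "The Week 3 (Day 15) pre-dose timepoint will not be included in the model assessing change", and gives the reason: "since this is expected to be similar to a baseline level of PPi after the first non-dosing period".

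LOCF enters in two places. The supportive exact Wilcoxon test in SAP 7.2.1 is run "using both last observation carried forward (LOCF) and observed case (OC) methods", and the sensitivity ANCOVA in SAP 7.2.1.5 is run "using both LOCF and OC methods in the FA Set". The matching PLP and Per Protocol Set runs follow the same pattern. The source of the carried value is set in SAP 7.2.1.1: "Missing values at the pre-3rd dose Week 9 assessment will be imputed with the last available on-treatment pre-dose trough assessment". Protocol 11.5.1 also prescribes LOCF for a missing primary endpoint value and does not restrict the source at all.

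Three places bear on the word trough:

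- The note to SAP Table 3 (Appendix 9.1): "Trough is defined as pre-dose concentration (ie, concentration data-point collected just prior to the next dose".
- The rows of that table, which attach a trough label to Days 29, 43, 50 and 61 but not to Days 15, 22 or 57. The Week 9 row, for instance, has only "Day 57: pre-dose".
- SAP 7.2.1, which describes all model timepoints from Day 22 to Day 61 as pre-dose troughs.

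The calendar is fixed by footnote 2 to Protocol Table 3: "the multiple dosing in Week 3 through Week 9 must be administered on Mondays, Wednesdays, and Fridays".

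**The concern.** The rule can be read three ways. Under the Table 3 note, any pre-dose sample is a trough, so Day 15 could be carried forward although it follows a single dose by two weeks. Under the row labels, a patient missing only Day 61 would receive Day 50 and not Day 57. Under SAP 7.2.1, Days 22 to 57 qualify. Two programmers could therefore fill the same gap with different samples.

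There is also a timing question. Day 61 is a Friday sample after a Wednesday dose, while all earlier multiple-dose troughs are Monday samples after a Friday dose. If PPi recovers over the extra day, a carried value understates the fall in that patient's cohort. The mixed model handles this through its categorical visit effect, but a carried value has no such adjustment.

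At stake is the credibility of the LOCF Wilcoxon result. It was the protocol's primary analysis, SAP 4.1 moved it to a supportive role, and readers may use it to judge whether that move matters. With about nine patients per cohort, one odd value can be visible.

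**Working it through.** **1. The plan's own figure.** Inputs from SAP 9.2: difference 2.3 µM, SD 1.5 µM, 9 per cohort; and 3.2 µM, SD 1.5 µM, 6 per cohort; two-sided 0.05. Noncentrality is (difference/SD) × √(n/2).

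- n = 9: (2.3/1.5) × √4.5 = 3.25 on 16 df, power 86.3% (stated: above 80%).
- n = 6: (3.2/1.5) × √3 = 3.70 on 10 df, power 91.4% (stated: above 90%).

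Both statements hold per comparison. The exact Wilcoxon test at the n = 9 design values has power of about 81 to 82% by simulation, which is the reference for step 5.

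**2. Hours since the last scheduled dose.** Day 1 is a Monday; doses fall on Day 1 and then on Monday, Wednesday and Friday from Day 15 to Day 61. Hours = 24 × (sample day − last dose day).

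| Sample | Last dose | Hours |
|---|---|---|
| Day 15 | Day 1 | 336 |
| Day 22 | Day 19 | 72 |
| Day 29 | Day 26 | 72 |
| Day 43 | Day 40 | 72 |
| Day 50 | Day 47 | 72 |
| Day 57 | Day 54 | 72 |
| Day 61 | Day 59 | 48 |

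The timing mismatch is real. No scheduled pre-dose sample before Day 61 is a 48 h trough, so no choice of source days removes it.

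**3. Where the readings part.** The rule takes the latest eligible value. The note reading (Days 15 to 57) and the model reading (Days 22 to 57) therefore give the same value for any patient with at least one of Days 22, 29, 43, 50 or 57. They differ only when all five are missing. The label reading differs mainly by taking Day 50 in place of Day 57; both are 72 h samples within the thrice-weekly dosing period.

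**4. Movement of a cohort mean.** Movement = number imputed × shift / cohort size. The documents give neither the 48 h to 72 h shift nor a missing rate, so the shift of 0.25 to 1.0 µM is an assumption; it could also be nil.

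- One of nine: 0.25/9 = 0.03 to 1.0/9 = 0.11 µM.
- Three of nine, the loss that leaves the planned minimum of six completers: 3 × 0.25/9 = 0.08 to 3 × 1.0/9 = 0.33 µM.
- One Day 15 value where the true change is −3 µM (assumption): 3/9 = 0.33 µM, or 3/6 = 0.50 µM with six per cohort.

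Equal numbers imputed with the same shift in both cohorts cancel in the difference of means.

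**5. Effect on the supportive Wilcoxon test.** Simulation, normal changes, assumed cohort means −3.0 and −0.7 µM, SD 1.5 µM, nine per cohort, exact two-sided test at 0.05.

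| Case | Power | Hodges-Lehmann shift (µM) |
|---|---|---|
| Complete, 9 v 9 | 81–82% | −2.30 |
| Observed case, one high-dose patient missing (8 v 9) | 81% | −2.29 to −2.30 |
| One high-dose value shifted +0.25 µM | 80% | −2.27 |
| One high-dose value shifted +1.0 µM | 77% | −2.19 to −2.20 |
| One value in each cohort shifted +1.0 µM | 80% | −2.30 |
| Day 15 carried, high-dose patient, mean change 0 | 63% | −2.03 to −2.04 |
| Day 15 carried, high-dose patient, mean change −0.7 µM | 68% | −2.07 |
| Day 15 carried, low-dose patient, mean change 0 | 84% | −2.38 |

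A 72 h source costs at most a few points of power in a supportive test. Only the Day 15 rows for a high-dose patient show a large loss, and those need five missing samples in that one patient. The direction depends on which cohort the patient is in: a low-dose Day 15 value widens the contrast.

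**The case for a change.** The strongest case for a change is that the LOCF Wilcoxon was the protocol's primary analysis and should be reproducible from the text alone. The text does not list the days, and a patient missing only Day 61 is an ordinary occurrence, so the choice between Day 50 and Day 57 is not confined to rare patients. A sentence would settle it at almost no cost. Observed case could also be named as the leading supportive result, so that a carried 72 h value never leads.

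What stands: the day list is absent, and the Table 3 note read alone would let Day 15 in. Full Analysis Set entry needs only one on-treatment PPi, so such a patient could be present.

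What does not stand: the label reading conflicts with SAP 7.2.1, the parent of the missing-data subsection, which treats every timepoint from Day 22 to Day 61 as a pre-dose trough, including the unlabelled Days 22 and 57. That section refers to Day 15 only as a pre-dose timepoint and explains why it is set aside. An analyst working from the section as a whole would reach Days 22 to 57. Ranking observed case above LOCF is a matter of preference: it moves further from the protocol and favours patients with a Day 61 value, who may differ from the others. The paired runs already show any gap between the two. A footnote on the 72 h interval would disclose the mismatch, not remove it.

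**Conclusion.** No change to the plan follows. The missing day list is a gap that analysts would fill sensibly from SAP 7.2.1 when writing the programming specification. The 72 h against 48 h difference is built into the sampling schedule and comes with any carry-forward here. Keeping both LOCF and observed case is a fair trade-off between continuity with the protocol and use of measured values only.

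No success criterion depends on LOCF: SAP 7.2.1 and 7.2.1.4 tie success to the two cohort comparisons, tested in the mixed model, which does not impute. For one imputed high-dose patient, an assumed 0.25 to 1.0 µM rise between 48 h and 72 h takes the power of the supportive Wilcoxon test from 81% (observed case) to between 80% and 77%. The larger loss with a Day 15 value (63% to 68%) requires a high-dose patient with no pre-dose PPi on Days 22 to 57, and rests on an assumed Day 15 change of 0 to −0.7 µM.

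These sizes assume normal changes, SD 1.5 µM and nine per cohort; the true 48 h to 72 h shift and the missing rate are not in the documents. If many Day 61 values were missing in one cohort only, the LOCF and observed-case results could separate visibly, and the planned side-by-side presentation would show it.
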